**Table 2 – Vital Sign Criteria for Abnormalities**

Vital Sign Criteria for Abnormalities	Criteria for Abnormalities (any of the following situation)
Systolic blood pressure	value < 80 mmHg value > 129 mmHg
Diastolic blood pressure	value < 60 mmHg value > 80 mmHg

Vital signs data and clinically relevant abnormalities in vital signs will also be listed.

#### 4.12.4.2 CCI

CCI  
CCI  
CCI  
CCI  
CCI

#### 4.12.4.3 Electrocardiograms

TriPLICATE 12-lead ECGs will be performed at timepoints as specified in the SoA (see protocol). ECGs should be obtained after the patient has been in a supine position for 5 minutes and recorded while the patient remains in that position. Mean QT intervals corrected for heart rate should be calculated using Fridericia's formula (QTcF).

The following variables will be recorded:

- PR interval (msec)
- RR interval (msec) – In case RR is not recorded, then RR will be calculated as 60/HR.
- QRS complex (msec)
- QT interval (msec)
- QTcF interval (msec)
- 

Mean of the 3 measures (considering 1 decimal) will be considered at each timepoint (Pre-dose, 1-hour dose, 12-hour dose ).

ECGs will be performed 3 times and an overall evaluation will be provided, as follows:

- Overall ECG evaluation (normal, abnormal – not clinically significant, abnormal – clinically significant)

A shift table of baseline QTcF to worst on-treatment results will be presented. For rating the worst on-treatment value, the following categories will be used based on the varying degrees of abnormality above, in the order of least to most severe (top to bottom):

- Missing result
- $\leq 450$  msec (i.e., 'normal')
- $> 450-\leq 480$  msec
- $> 480-\leq 500$  msec
- $> 500$  msec

Baseline QTcF will be the pre-dose value at baseline. Worst on-treatment QTcF will be the worst post-baseline all timepoints considered.

All ECG parameters will be listed.

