#### 4.12.4 Vital Signs, Physical Examinations and Other Observations Related to Safety

##### 4.12.4.1 Vital Signs

The following vital signs will be recorded at baseline and post-baseline visit:

- Weight (kg)
- Temperature (°C or °F)
- Systolic blood pressure (in mmHg)
- Diastolic blood pressure (in mmHg)
- Pulse rate (beats/minute)
- Respiratory rate (breaths per minute)
- BMI
- O2 Saturation

A shift table from baseline systolic blood pressure and diastolic blood to worst on-treatment results will be presented. The normal/abnormal classification will be made using the criteria defined in table below:

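### SAP 4.12.4.3 reports RR in msec but calculates a missing RR as 60/HR, which is in seconds, so calculated RR values are 1000 times too small for their label

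*SAP*

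**What the plan says.** SAP section 4.12.4.3 lists the ECG variables to be recorded. All of them are intervals in msec: PR, RR, QRS, QT and QTcF. The RR entry carries its own fallback: "In case RR is not recorded, then RR will be calculated as 60/HR". The section gives no unit for HR; the SAP's abbreviation list only expands it as heart rate.

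Three other statements in the section bear on how a calculated RR would be used:

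- On averaging: "Mean of the 3 measures (considering 1 decimal) will be considered at each timepoint".
- On correction for heart rate: "Mean QT intervals corrected for heart rate should be calculated using" Fridericia's formula. Protocol section 8.2.4 has the same instruction. Neither document writes out the equation or says which unit of RR it takes.
- On reporting: "A shift table of baseline QTcF to worst on-treatment results will be presented", with a top category above 500 msec. RR has no shift table, but every ECG parameter goes into the listings.

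**The concern.** The label and the formula for RR use different units. A programmer who applies the rule exactly as written puts seconds into a field that otherwise holds milliseconds. That makes the RR listing inconsistent from row to row and distorts any triplicate mean that combines the two kinds of value.

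A second possible effect is on QTcF, the one ECG measure with its own safety table. The Fridericia correction needs RR, and the SAP leaves open whether analysts will ever recompute QTcF from it. If they do, the unit they assume for the calculated RR decides whether the result is right. The shift table takes the worst post-baseline value over all timepoints, so a single wrong timepoint would set a patient's category.

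**Working it through.** **Inputs**

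- RR unit (msec) and fallback rule (60/HR): SAP 4.12.4.3.
- HR in beats per minute: assumed. SAP 4.12.4.1 gives pulse rate in beats per minute, which supports this.
- Fridericia's formula: QTcF = QT / RR^(1/3) with RR in seconds. This is the standard form; the documents name the method only.
- QT 400 msec and HR 75: illustrative values, not from the documents. Heart rates of 50, 60 and 100 were also checked.

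**Step 1: the RR rule.** One minute is 60 seconds or 60000 msec, so RR is 60/HR in seconds and 60000/HR in msec.

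| HR (beats/min) | SAP rule, 60/HR | RR in msec, 60000/HR | Ratio |
|---|---|---|---|
| 50 | 1.2 | 1200 | 1000 |
| 60 | 1.0 | 1000 | 1000 |
| 75 | 0.8 | 800 | 1000 |
| 100 | 0.6 | 600 | 1000 |

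The factor is exactly 1000 at any heart rate.

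**Step 2: the triplicate mean.** At HR 75, with two RR values recorded as 800 and one calculated by the rule, the mean is (800 + 800 + 0.8)/3 = 533.6 msec. The correct mean is 800 msec.

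**Step 3: QTcF, if it is re-derived from RR.** The correct value at QT 400 msec and HR 75 is 400/0.8^(1/3) = 430.9 msec. The result depends on how the program handles the calculated RR:

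- *Used directly as seconds:* 400/0.8^(1/3) = 430.9 msec. No error.
- *Read as msec and divided by 1000, single ECG:* 400/0.0008^(1/3) = 4308.9 msec. This is 10 times too large, because 1000^(1/3) = 10. The ratio is the same at all four heart rates.
- *Read as msec, computed from the triplicate mean with one calculated RR:* 400/0.5336^(1/3) = 493.2 msec. This would move the patient from the category up to 450 msec into the one above 480 and up to 500 msec.

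**Step 4: does the SAP send QTcF down any of these paths?** It lists QTcF among the recorded variables and nowhere says that QTcF is recomputed from a calculated RR.

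**The case against.** A reader might infer from the rule that every QTcF resting on a calculated RR will be ten times too large and that the QTcF shift table will therefore be wrong. The documents do not support that. Fridericia's formula takes RR in seconds, and 60/HR is RR in seconds, so direct use gives the right answer. The tenfold error needs a further division by 1000 that the SAP does not mention. QTcF is listed as recorded, and the Fridericia instruction in protocol 8.2.4 sits among directions for taking ECGs at the site. That fits QTcF arriving already computed, though the wording does not settle it. This part of the objection stands, and the QTcF effect is conditional.

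It can also be said that the error would be noticed: an RR of 0.8 beside values near 800, or a QTcF above 4000 msec, is impossible on its face, and SAP 4.1 requires independent checking of outputs. That stands for single values. It is weaker for means, since a mean RR of 533.6 msec or a QTcF of 493 msec does not look impossible.

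Nor do the documents tie the rule to larger decisions. The QTcF limit in the core exclusion criteria (protocol 5.4) is applied at screening, and the exploration of QTc prolongation in protocol 2.3.1.2 is a future population PK analysis outside this SAP.

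None of this removes the mismatch between the msec label and the formula.

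**Conclusion.** The RR rule is wrong as written. Given HR in beats per minute, a calculated RR is 1000 times too small for its stated unit. The effect that follows from the text is on the RR listing and on triplicate RR means that mix recorded and calculated values (533.6 instead of 800 msec in the example).

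An effect on QTcF needs two further conditions, neither of which the SAP states: QTcF is re-derived from RR, and the program takes the calculated RR as msec. If both hold, the example gives 4309 against 431 msec for a single ECG, or about 493 against 431 msec from a triplicate mean with one calculated RR.

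The documents do not say how often RR will be missing, so the number of affected records cannot be estimated. This is a minor correction. It does not touch the efficacy analyses or the design.

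**What to change.** Replace the fallback in SAP 4.12.4.3 with: if RR is not recorded, RR (msec) = 60000/HR, with HR in beats per minute.

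Add one sentence on QTcF: the recorded QTcF is used where available, and any QTcF re-derived by the analysts uses QT / (RR in msec / 1000)^(1/3).

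The cost is two lines of SAP text and a check that the ECG program matches them. Nothing changes in data collection or in the shift-table categories.

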#### 4.12.4.4 Karnofsky Performance Status - **Module 1 only**

Karnofsky performance status will be assessed at the times specified in the SoA based on the following (see protocol) **for module 1**:

100. Normal no complaints
90. Able to carry on normal activities. Minor signs or symptoms of disease
80. Normal activity with effort
70. Care for self. Unable to carry on normal activity or to do active work
60. Requires occasional assistance, but able to care for most of his/her needs
50. Requires occasional assistance and frequent medical care
40. Disabled. Requires special care and assistance
30. Severely disabled. Hospitalisation indicted though death non-imminent
20. Very sick. Hospitalisation necessary. Active supportive treatment necessary
10. Moribund

A shift table will be presented to show worst changes from baseline. Karnofsky score results will be listed by visit.

#### 4.12.4.5 Eastern Cooperative Oncology Group Performance Status (ECOG) - **Module 2&3 only**

ECOG performance status will be assessed **for module 2&3** at the times specified in the SoA based on the following (see protocol):

0. Fully active; able to carry out all usual activities without restrictions
1. Restricted in strenuous activity, but ambulatory and able to carry out light work or work of a sedentary nature (e.g. light housework or office work)
2. Ambulatory and capable of self-care, but unable to carry out any work activities; up and about more than 50% of waking hours
3. Capable of only limited self-care; confined to bed or chair more than 50% of waking hours
4. Completely disabled; unable to carry out any self-care and totally confined to bed or chair
- 5 Dead

A shift table will be presented to show worst changes from baseline. ECOG score results (including screening value) will be listed by visit.

#### 4.12.4.6 Bone Evaluation

Blood Sample for Bone Turnover Biomarkers (beta C-terminal cross-linked telopeptide of type I collagen [b-CTX]) and dual-energy x-ray absorptiometry (DXA) scan assessments will be performed at timepoints as specified in the SoA (see protocol). The following variables will be collected:

- CCI

CCI [REDACTED]

#### 4.12.4.7 Bones Evaluation variables will also be listed. Physical Examination

Physical Examination will be assessed at the times specified in the SoA. By-patient listing will be provided for all patient in FAS by visit, including details in abnormalities if any.

#### 4.12.5 Safety Monitoring Committee

A safety monitoring committee (SMC) will be appointed to review safety data from patients in this study and a parallel study in CRC. The SMC is a group consisting of the country principal investigators (PI) from each of the phase 2 studies and a statistician. An independent bone metabolism consultant will review the data and provide expert advice to the SMC meetings, but will not be a formal member of the SMC. The SMC will be convened to review the safety and tolerability of RXC004 at regular intervals.

The first data review meeting will be scheduled to occur when approximately █ patients have received at least 1 cycle of treatment across the two studies and subsequent meetings will be held every 6 months until the phase 2 studies close or last patient discontinues study treatment (whichever occurs first). Additional safety reviews may be performed at other times as deemed appropriate by the Sponsor or SMC.

Since the studies are open label, there are no blinding issues associated with performing interim safety reviews. Full details of the SMC procedures, processes, and analyses can be found in the SMC Charter.

#### 4.13 Tertiary Analyses

CCI

CCI

CCI

CCI

CCI

CCI

#### 4.14 Exploratory Analyses

CCI

#### 4.15 Determination of Sample Size

The method by Frewer et al (**Error! Reference source not found.**), together with the totality of the data collected, will be used to guide go/no-go decision making:

##### Module 1

For the population under investigation, the standard of care of liposomal irinotecan in combination with 5-FU/Leucovorin reported a 6 month PFS rate of **CCI**% (NAPOLI-1 trial, **Error! Reference source not found.**). This level of **CCI**% will be the **CCI**. An improvement to **CCI**% in 6 month PFS rate would be considered clinically significant in this patient population (**CCI** **CCI** – **CCI**%). Statistically, the hypothesis that will be tested is  $H_0: p \leq \text{CCI}$  versus  $H_1: p > \text{CCI}$ , where  $p$  is the proportion of patients who live 6 or more months without disease progression. **CCI**

**CCI**  
**CCI**  
**CCI**. If **CCI** or less are progression free at 6 months RXC004 would be determined not worthy of further investigation with this patient population. The type I and II error rates associated with this testing are 0.06 and 0.10, respectively. The PFS at 6 months estimates will be used to guide the decision for onward development. The totality of the data, including the results from the secondary endpoints will be used to in the final decision.

Approximately **CCI** patients are expected to be enrolled in order for **CCI** patients to be evaluable.

##### Module 2

If the true PFS at 6 month rate with RXC004 were **CCI**% or less, there is limited interest in developing RXC004 further in this population **CCI**%). This level is estimated from the ABC-06 trial with mFOLFOX where the median PFS was **CCI** and DCR was **CCI**% (Lamarca et al 2019). A 6 month PFS rate of **CCI**% would be considered to be a clinically significant improvement **CCI**%). Statistically, the hypothesis that will be tested is  $H_0: p \leq \text{CCI}$  versus  $H_1: p > \text{CCI}$ , where  $p$  is the proportion of patients who live 6 or more months without disease progression. **CCI**

**CCI**

CCI

CCI

If [REDACTED] or less are progression free at 6 months RXC004 would be determined not worthy of further investigation with this patient population. The type I and II error rates associated with this testing are 0.06 and 0.20, respectively. The PFS at 6 months rate will be used to guide the decision for onward development. The totality of the data, including the results from the secondary endpoints will be used to in the final decision.

Approximately CCI patients are expected to be enrolled in order for CCI patients to be evaluable.

### Module 3

In the KEYNOTE-158 and KEYNOTE-028 studies, a combined response rate of approximately CCI% has been observed (Piha-Paul et al 2020), thus an improvement to CCI% would be clinically significant and is used as the CCI in setting the go/no-go hurdles in terms of an efficacy rate that would not want to be missed. CCI

CCI

CCI

#### 4.16 Changes in the Conduct of the Study or Planned Analysis

After an ongoing review of the available data the following changes to the final outputs were made compared to the protocol:

- Medical History will not be summarized but will be listed.
- CCI
- Overall Survival will not be summarized but will be listed.

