Percentage change in tumour size will be derived at each visit by the percentage change from baseline in the sum of diameters of target lesions. The best percentage change in tumour size

will be the patient's value representing the largest decrease (or smallest increase) from baseline in tumour size. Best percentage change in tumour size will be presented in waterfall plots and percentage change in tumour size at each visit will be presented in a spider plot.

Overall survival is defined as the time from first day of study treatment until death due to any cause. Any patient not known to have died at the time of analysis will be censored based on the last recorded date on which the subject was known to be alive. Overall survival will be listed by patient and presented graphically using Kaplan-Meier plots. Median, 6 month and 12 month OS rates will be estimated.

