### 3.2.1.8 Overall Survival

OS is defined as the time from the first day of study treatment (C0D1) until death due to any cause. Any patient not known to have died at the time of analysis will be censored based on the last recorded date on which the patient was known to be alive. OS time is defined as:

OS (days) = Date of death or last contact – first dose of study treatment (C0D1) + 1

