#### **4.2.4 End of Study (EoS)**

A patient is considered to have completed the study if he/she has completed all phases of the study (including the last visit and the last scheduled assessment shown in the SoA) or withdraws consent whichever occurs first.

The EoS is defined as the date of the last visit of the last participant in the study or the last scheduled assessment shown in the SoA for the last participant in the study before the data cut off (DCO). The study data is planned to be analysed and reported based on all patient data at the primary completion data cut-off date (approximately 24 weeks after cycle 1 day 1 for the last patient in), or at the End of Study, whichever comes first.

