#### 4.7 Medical History and Surgical History

Medical history and Surgical history as pre-specified in the Medical and Surgical history eCRF will be presented in the patient data listings.

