#### 4.11.2.1 Progression Free Survival

PFS is defined in Section 3.2.1.1.

Kaplan-Meier analyses will be conducted for each module. Survival plots will be produced to present Kaplan-Meier estimated curves. In addition, the following parameters estimated from the Kaplan-Meier curves will be provided for each group:

- Median PFS and corresponding 95% CIs
- PFS rate at 3, 6 and 12 months and corresponding 90% CIs and 95% CI (one month = 30.4375 days).

PFS will be listed for all patients in the FAS.

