#### 4.11.3.2 Overall Survival

OS is defined in Section 3.2.1.8.

Kaplan-Meier analyses will be conducted on the FAS. Survival plots will be produced to present Kaplan-Meier estimated curves.

OS will be listed for all patients in the FAS.

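### SAP 4.16 reduces overall survival to a listing while SAP 4.11.3.2 still plans Kaplan-Meier curves, and neither section specifies the median, 6-month and 12-month OS that the protocol promises

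*SAP*

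**What the plan says.** **Protocol.** Section 3 lists OS as a secondary endpoint for Modules 1, 2 and 3, and SAP section 2 repeats this. Protocol 9.4.2.2 plans three kinds of OS output: a by-patient listing, Kaplan-Meier plots, and numerical estimates ("Median, 6 month and 12 month OS rates will be estimated").

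**SAP, body text.** Section 3.2.1.8 defines the OS variable and a censoring rule that uses the latest date of confirmed survival: "Any patient not known to have died at the time of analysis will be censored based on the last recorded date". Section 4.11.3.2 then says: "Kaplan-Meier analyses will be conducted on the FAS. Survival plots will be produced to present Kaplan-Meier estimated curves". It adds a listing on the full analysis set (FAS) and stops there.

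**SAP, changes section.** Section 4.16 opens with "After an ongoing review of the available data the following changes to the final outputs were made compared to the protocol". One of its bullets reads: "Overall Survival will not be summarized but will be listed". Another makes the same change for medical history.

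**SAP, PFS for comparison.** Section 4.11.2.1 names the median with a 95% CI and "PFS rate at 3, 6 and 12 months and corresponding 90% CIs and 95% CI".

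**The concern.** There are two separate problems.

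First, 4.16 and 4.11.3.2 do not say the same thing about OS. A programmer working from the SAP cannot tell whether a Kaplan-Meier curve is to be produced.

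Second, the protocol's numerical OS estimates have gone, and the stated ground is a look at the data. The study is open label. The visible text does not say whether OS outcomes were part of that review, and the visible revision-history entries do not record when the decision was taken. A reader therefore cannot exclude that a secondary endpoint was dropped because of how it looked. Nothing in the documents shows that it was.

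What is at stake is the evidence for onward development. SAP 4.15 (Modules 1 and 2) and Protocol 12.11.1 (Module 3) say the final decision rests on all the data, secondary endpoints included. A listing with censored times leaves each reader to construct their own OS estimate.

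**Working it through.** **Step 1: which OS outputs survive under each reading**

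| OS output | Protocol 9.4.2.2 | SAP 4.11.3.2 alone | SAP 4.16 read as listing only | SAP 4.16 read as no tables, figures kept |
|---|---|---|---|---|
| Listing | yes | yes | yes | yes |
| Kaplan-Meier curve | yes | yes | no | yes |
| Median OS | yes | not named | no | no |
| 6-month OS | yes | not named | no | no |
| 12-month OS | yes | not named | no | no |

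The last three rows are empty in every SAP column. The count is 3 estimates × 3 modules = 9, or 3 × 4 = 12 if Module 2 Cohort 2 opened and is reported separately.

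**Step 2: which reading is more natural**

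The parallel medical-history bullet in 4.16 matches SAP 4.7: "Medical history and Surgical history as pre-specified in the Medical and Surgical history eCRF will be presented in the patient data listings". There, not summarised means listing only, which favours the same meaning for OS. Against that, SAP 4.2.6 and 4.2.7 treat summaries and figures as separate output types, so a curve could survive. The text does not settle it.

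**Step 3: would OS be too immature to estimate? (Modules 1 and 2)**

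- Cut-off (SAP 4.2.4): "approximately 24 weeks after cycle 1 day 1 for the last patient in", that is 168 days from C1D1.
- OS runs from C0D1, and Cycle 0 lasts 3 to 7 days (schedules of assessments). Minimum follow-up is therefore 168 + 3 = 171 to 168 + 7 = 175 days, or 5.62 to 5.75 months at the SAP's 30.4375 days per month.
- Six months is 6 × 30.4375 = 182.6 days, so the last patient falls only 8 to 12 days short.
- Medians quoted in the protocol: 3 to 7 months for second-line pancreatic cancer (10.1), and 6.2 months for mFOLFOX in biliary cancer (11.1).

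Assume exponential survival. The share of last-enrolled patients dead by day 171 is 1 − 0.5^(5.62/median), and 6-month survival is 0.5^(6/median):

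| Assumed median (months) | Dead by day 171 | Alive at 6 months |
|---|---|---|
| 3 | 72.7% | 25.0% |
| 6.2 | 46.6% | 51.1% |
| 7 | 42.7% | 55.2% |

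Earlier-enrolled patients have longer follow-up.

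**Step 4: would the median be reached?**

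Module sizes are redacted, so n = 15 to 30 is an assumption.

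- *Uniform accrual, by simulation.* Over medians of 3 to 7 months, the Kaplan-Meier median is reached in at least about 80% of runs with 6 months of accrual and at least about 95% with 12 months.
- *Worst case, everyone enrolled at once.* The median is reached only if at least half have died by day 171, so the probability is P(Binomial(n, p) ≥ n/2), with p = 0.466 or 0.427. At n = 15 (8 or more deaths) this is 40% or 28%. At n = 30 (15 or more) it is 43% or 26%. Over all n from 15 to 30 it runs from 21% to 49%.

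**Step 5: precision of a 6-month rate**

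Exact 95% CI, with about half alive at 6 months and no earlier censoring: 7/15 gives 21.3% to 73.4%, and 15/30 gives 31.3% to 68.7%.

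**The case against.** The strongest counter-reading is that the sections do not conflict. SAP 4.11.3.2 keeps the curve and the listing and omits exactly the numerical estimates, while 4.16 announces that OS is not summarised. If that word means summary tables, the two sections fit together, and approximate medians and landmark rates can be read off the curve. The change is openly declared in the section meant for it. OS carries no hypothesis and no hurdle, and the modules are single-arm. One bullet in 4.16 is redacted, so the visible reason may not be the whole record. The maturity argument rests on assumed survival, accrual and module size. The cut-off can also come sooner if the study ends early, and Module 3 has a different cut-off in Protocol 9.4.1, so the calculation does not cover it.

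Much of this stands. The curve-kept reading is possible, the maturity figures are only context, and an inference of selective reporting would be unsupported. None of it restores the estimates, however. A value read off a curve has no confidence interval and is not the analysis the protocol specifies, and the SAP nowhere says that the curve-kept reading is intended.

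**Conclusion.** The concern holds, and it should be fixed. The visible OS text is intact at each place relied on, so this is not a product of redaction. The SAP leaves median, 6-month and 12-month OS unspecified in every module under any reading, and leaves it unclear whether a curve will be produced. The reason visible in 4.16 does not say whether OS results were seen.

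The consequence is limited. The formal criteria on 6-month PFS and ORR are unaffected. What is lost is a usable estimate of a secondary endpoint that is meant to inform the development decision.

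Immaturity does not evidently justify the omission in Modules 1 and 2. At the planned cut-off nearly all patients would have 6-month follow-up, and the median would probably be reached unless accrual was very compressed. Protocol 8.1.2 also provides for survival contact within 7 days of the cut-off for any survival analysis. The 12-month rate could well be immature. These statements assume exponential survival at the protocol's quoted medians, n of 15 to 30, and no early study closure. The textual finding needs none of those assumptions.

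**What to change.** Delete the OS bullet from SAP 4.16. In 4.11.3.2, name the Kaplan-Meier median OS and the 6- and 12-month OS rates on the FAS, with confidence intervals in the form 4.11.2.1 uses for PFS, by module and by Module 2 cohort if Cohort 2 opened. Add a sentence that estimates immature at the cut-off will be reported as such.

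If the sponsor prefers to keep the bullet, 4.16 should give a dated reason that does not rest on OS results and should state whether curves are kept. Section 4.11.3.2 should then be made to agree.

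The cost is one Kaplan-Meier table per module on data already collected and a variable already defined. The downside is imprecision: a median may not be reached, and intervals may be as wide as those in the working above.
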